Ciprofloxacin Versus Levofloxacin in Stem Cell Transplant

NCT03850379

Study protocol March 14, 2018

4. **SIGNIFICANCE:** State concisely the importance of this project by relating the purpose to broader, long-range objectives. This selective intervention will establish a unique setting to assess the efficacy of the use of levofloxacin vs ciprofloxacin prophylaxis in patients undergoing SCT

5. **SUBJECTS IN THE PROJECT:**

- State the inclusion and exclusion criteria for enrollment of subjects. **Eligibility Criteria:** Patients 18-75 years of age with a diagnosis of a hematological malignancy. Meet the BMT program criteria to undergo hematopoietic stem cell transplantation.
- Describe the control population (if utilized) and justify its selection. **NA**
- Support the likelihood of recruiting the number of subjects required to complete the project. Relate this to other projects recruiting similar subjects. In our growing program we have been doing almost 100 SCT per year and all need prophylaxis antibiotics to prevent infection

6. **PROJECT DESIGN AND PROTOCOL:**

- Describe the experimental design/methodology. This is a prospective study comparing consecutive patients who will be receiving ciprofloxacin prophylaxis vs. levofloxacin prophylaxis for SCT till engraftment defined as ANC >1000,

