- Discuss potential limitations and difficulties in the protocol. Uncontrolled multi-variables and their contribution to patient's disease course may attenuate the results. Sorting and stratifying each variable may create multiple small groups of patients which may not possess the power to reflect and determine differences among those small groups
- Provide a tentative schedule for conducting and completing this project and, if applicable, the multicenter study. We do around 100 SCT per year, so we will need 3 years to recruit the patients and 4 years to finalize the data
- Data collection: Submit a copy of the data collection tool or list the data fields to be collected (review IRB policy, *Access to Medical Records for Research*). attached

7. **DATA ANALYSIS:** Describe the analysis of the data and relate this to the specific aims in detail. Case reports and medical record reviews also require a description of the planned data analysis (ie. descriptive, observational). The Committee recommends free consultation with the Division of Biostatistics and Research Epidemiology before IRB submission. **Number of pts needed:** to prove 10% improvement in overall bacterial infections control (Decrease from 20% to 10%), need 308 pts; 154 in each group To achieve 70% power. Data will be collected and analyzed. We will prospectively follow patients who will get

HSCT. Objectives are to explore the impact of cipro vs levo on Incidence of bacteremia and incidence of resistant and non-resistant gram-positive strains bacteremia. Also impact of Levo vs Cipro incidence of Clostridium difficile and GVHD Demographics, disease-related and transplant-related variables mentioned above will be collected. A two sample test of proportion equality will be used as the test for the primary aim. PFS is defined as the time from HSCT to the time of progression, death or last contact whichever occurred first. OS is defined as the time from HSCT to the time of death or last contact. OS and PFS will be estimated using the Kaplan-Meier method.

8. JUSTIFICATION FOR NUMBER OF SUBJECTS OR DATA:

- State the number of subjects or data points to be analyzed in the project at this institution and the total number for multicenter studies. The Committee recommends consultation with the Division of Biostatistics and Research Epidemiology [contact]. 2. The target sample size is 308 patients. Accrual Period: 3 years.

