 Yes  No	14. Is there an IND #? If 'yes', is this an (check which one applies):  investigational drug/substance  approved drug being investigated to provide data to the FDA in support of a new indication or to change the labeling
 Yes  No	15. Have restrictions been placed on the use of this drug/substance by the FDA? If yes, describe them: Fluoroquinolones have been associated with disabling and potentially irreversible serious adverse reactions that have occurred together, including: tendinitis and tendon rupture, peripheral neuropathy, and CNS effects. Discontinue ciprofloxacin immediately and avoid the use of fluoroquinolones in patients who experience any of these serious adverse reactions.
 Yes  No	16. Are other drugs/substances known to interact in important ways with the investigational agent being tested in this protocol? If yes, list the drugs/substances (and/or their categories) and describe the precautions for avoiding adverse events resulting from such interactions: Fluoroquinolones may prolong QTc Interval same as antifungal azoles but we assess ECG and QT Interval in all out SCT pts and use alternatives when QT is prolonged
 Yes  No	17. Is the drug/substance to be used in children? If yes, has it been approved for use in these subjects?
 Yes  No	18. Is the drug/substance to be used in pregnant women? If yes, has it been approved for use in these subjects?
 Yes  No	19. Will the dosage/schedule be modified within the protocol in response to efficacy or side effects? If yes, what end points will drive the dosage alterations? drug will be discontinued and alternative prophylaxis will be used in the event of unacceptable toxicity per our ID transplant protocol Azithromycin 250 mg PO QD
 Yes  No	20. Is compliance with dosage schedule monitored? If yes, how? P2 nurse giving the medication and documenting in MAR

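### Does a three-year accrual period at about 100 transplants a year leave the study short of its 308 patients?

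*Combined protocol and SAP*

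**What the plan says.** The sample size appears in sections 7 and 8 of the combined protocol and SAP: "need 308 pts; 154 in each group To achieve 70% power", for a fall in bacterial infection from 20% to 10%. On the analysis, section 7 says: "A two sample test of proportion equality will be used as the test for the primary aim". It gives neither alpha nor sidedness.

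Section 8 sets the target beside the time: "The target sample size is 308 patients. Accrual Period: 3 years".

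Transplant volume is described twice. Section 5 says "In our growing program we have been doing almost 100 SCT per year and all need prophylaxis antibiotics to prevent infection". Section 6, answering a form item that asks for a provisional timetable, says "We do around 100 SCT per year, so we will need 3 years to recruit the patients", and allows four years until the data are final.

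Entry is limited to ages 18 to 75 with a haematological malignancy and acceptance by the transplant programme. Form A adds, for each drug, that the centre will "use alternatives when QT is prolonged" (item 16) and that patients with unacceptable toxicity move to other prophylaxis (item 19). No rate of ineligibility, refusal or loss is given anywhere.

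**The concern.** The timetable is presented as a deduction: so many transplants a year, therefore three years. Multiplied out, the deduction gives 300 rather than 308, and section 5 puts the volume slightly below 100. The product also treats every transplant as one enrolled, analysable patient. Some recipients may fall outside the age or diagnosis limits, decline, be unable to take a fluoroquinolone, or be transplanted twice.

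The sample size has no reserve to absorb this, because 154 per group is the bare formula result. Planned power is only 70%, so there is little to lose. If the study closed at three years with materially fewer patients, a true halving of infection could be missed close to half the time. If it ran on to 308 instead, the four-year finish could be at risk.

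**Working it through.** **Inputs.** 20% versus 10%, 154 per group, 70% power (sections 7 and 8); 308 patients and 3 years (section 8); about 100 transplants a year (sections 5 and 6); primary endpoint read by day 60 (section 6). Assumed: two-sided 5% alpha.

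**1. Reproduce the plan's figure.** Unpooled normal formula:

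n = (1.960 + 0.524)² × (0.20 × 0.80 + 0.10 × 0.90) / 0.10² = 6.172 × 0.25 / 0.01 = 154.3 per group.

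This matches 154 per group and supports the assumed alpha. A one-sided 5% test at 70% power would need only 240 in total (pooled formula).

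**2. Accrual at a flat rate, every transplant enrolled.**

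| Transplants a year | Patients in 3 years | Years to 308 |
|---|---|---|
| 95 | 285 | 3.24 |
| 98 | 294 | 3.14 |
| 100 | 300 | 3.08 |
| 102.7 | 308 | 3.00 |

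At 100 a year the shortfall is 308 − 300 = 8, or 8/308 = 2.6%. The extra time is 0.08 × 12 = about 1 month.

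**3. Power at 300 against 308, by one formula.** Pooled-variance test:

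power = Φ{[0.10 − 1.960 × √(2 × 0.15 × 0.85 / n)] / √(0.25 / n)}

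- n = 154: (0.10 − 0.0798) / 0.0403 = 0.502, power 69.2%.
- n = 150: (0.10 − 0.0808) / 0.0408 = 0.470, power 68.1%.

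The loss is 1.1 points. Exact binomial calculation gives 69.9% and 68.6%, a loss of 1.3 points. Setting 68.1% against the nominal 70% would count a difference between formulas as an accrual loss.

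**4. Growth.** With 100 in year 1:

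- 2.7% a year: 100 + 102.7 + 105.5 = 308.

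From lower starting points:

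- 98 rising 5% a year: 98 + 102.9 + 108.0 = 309.
- 95 rising 5% a year: 299.
- 95 rising 10% a year: 314.

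Modest growth closes the gap from a start near 100. From 95 it takes more than 5% a year.

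**5. Chance variation.** If transplants arrive as a Poisson process with mean 300 over three years, the standard deviation is √300 = 17.3. A gap of 8 is under half of that, and the chance of reaching 308 anyway is 33%.

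**6. Incomplete enrolment.** The documents give no share, so these shares are assumptions applied to a flat 100 a year:

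| Share enrolled and analysed | Patients in 3 years | Power if stopped there | Years to 308 |
|---|---|---|---|
| 90% | 270 | 63.5% | 3.42 |
| 80% | 240 | 58.4% | 3.85 |
| 70% | 210 | 52.8% | 4.40 |

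The last two columns are alternatives. A study that runs on to 308 keeps its planned power.

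**7. The four-year finish, read as four years in total.** Adding 60 days (0.16 year) for the last patient's endpoint gives 3.08 + 0.16 = 3.24 years at full enrolment and 3.42 + 0.16 = 3.58 at 90%. At 80% it is 3.85 + 0.16 = 4.01. The finish is in doubt only at about 80% or lower.

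**The case for a change.** The strongest case for a change sets the eight patients aside and rests on the implied full enrolment. The plan itself names reasons why some transplants will not yield an analysable patient, yet allows for none. Growth then gives little relief: from 100 in year 1, reaching 308 in three years needs about 13.5% a year at 90% enrolment and 26% at 80%. Section 8 also gives the three years without qualification, and nothing says whether the number or the date governs.

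Part of this stands. There is no stated margin, and real accrual may well run past three years.

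The rest is weaker. The enrolment shares that produce the large losses are not in the documents, which describe consecutive patients, broad entry criteria and a need for prophylaxis in all. Form A item 19 concerns patients already enrolled, and nothing removes them from the analysis. Item 16 names azoles as well as fluoroquinolones as prolonging QT, so it does not say which drug is replaced, and it is not an exclusion criterion. No count of repeat transplants is given. On number against date, the natural reading is that 308 is the design quantity, since it alone is derived from the power requirement, and that three years is the estimate of how long it takes.

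**Conclusion.** No change to the plan is needed. Three years at 100 a year does fall 8 short of 308, but 2.6% is within the looseness of a volume stated only approximately, for a growing programme and in answer to a request for a provisional timetable. The consequence the documents support is about one month of extra recruitment or, if the study stopped at 300, about one point of power.

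Power of 53% to 64% requires two things the plan does not say: that 10% to 30% of transplants yield no analysable patient, and that accrual closes at three years regardless. A team that recruits to the stated 308 obtains the planned sample, test and power whether that takes 3.1 years or longer. Restating the timetable would therefore alter no estimate and no conclusion. The absence of a stated margin is worth knowing when progress is monitored.

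The power figures assume two-sided 5% and equal groups. The accrual figures assume one patient per transplant.

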- Outline the protocol, corresponding it to the specific aims; identify the data or endpoints to be analyzed to reach the specific aims. **Primary Objective:** to assess incidence of bloodstream bacterial infections in the ciprofloxacin group compared to levofloxacin group up to day 60 after SCT. **Secondary objectives:** To assess time to engraftment, incidence of Clostridium difficile infection, rate of febrile neutropenia, Incidence of Gram positive and gram negative bacterial breakthrough infections, inpatient mortality, rate of hypotension, ICU admissions, fungal infections. In allo SCT patients assess rate of acute graft versus host disease (GVHD) by day 60. Blood stream infections will be documented along with type of pathogen and drug resistance. Also C diff infection will be documented. Time of engraftment will be documented. Secondary objectives like GVHD, PFS, OS will be assessed using this regimen. PFS and OS were estimated from day 0 according to the Kaplan-Meier method. Estimates of treatment related mortality, acute GVHD and chronic GVHD rates will be based upon cumulative incidence estimates, treating relapse as a competing risk. Engraftment rates (and corresponding 95% confidence intervals) will be estimated by the proportion of patients who engraft. Neutrophil recovery is defined as a sustained absolute neutrophil count (ANC) > 0.5 x 10⁹/L for 3 consecutive days. Engraftment date is the first day of three (3) consecutive days that the ANC exceeds 0.5 x 10⁹/L. Delayed engraftment is defined as the evidence of engraftment beyond day 28 post SC infusion achieved after the administration of therapeutic (high dose) hematopoietic growth factors. Primary Graft failure is defined as failure to achieve an ANC > 0.5 x 10⁹/L for 3 consecutive days by day 28 post SC infusion, with no evidence of donor derived cells by bone marrow chimerism studies and no evidence of persistent or relapsing disease. Secondary graft failure is defined as a sustained decline of ANC < 0.5 x 10⁹/L for 3 consecutive days after initial documented engraftment with no evidence of disease progression. Autologous reconstitution is defined by the presence of ANC > 0.5 x 10⁹/L without evidence of donor-derived cells by bone marrow chimerism studies. This can occur at initial engraftment or later after initial engraftment has been documented. Complete remission (CR) is defined according to disease specific criteria as per the CIBMTR. Relapse defined according to disease specific criteria will be recorded by the day of detection.

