- Describe the statistical justification for this number of subjects or data points. after discussion with biostat to calculate Number of pts needed: to prove 10% improvement in overall bacterial infections control (Decrease from 20% to 10%), need 308 pts; 154 in each group To achieve 70% power.*

FORM A

HENRY FORD HEALTH SYSTEM (IRB) DRUG/SUBSTANCE INFORMATION

(This form must be completed for each individual drug or substance -*investigational or marketed*- that is being administered as part of this research study)

1. Generic/Chemical Name: Ciprofloxacin	2. Trade Name: Cipro
3. Manufacturer: Bayer	4. Mode of Administration: P.O. other: IV
5. How Supplied (dose form & strength): 500 mg	6. Who will be administer the drug/substance? P2 Nurse
7. Dosage and Schedule Proposed: 500 mg BID	
8. Will you be utilizing research pharmacy for storage or dispensing of any medication? (if this is an inpatient study, you are required to use research pharmacy).  Yes  No	
9. Describe the primary actions of the drug/substance: Prevnet infections in neutropenic patients by Inhibiting DNA-gyrase in susceptible organisms	
10. Describe the therapeutic benefit anticipated from the use of this drug/substance: Prevent infections in neutropenic patients after the conditioning regimen for SCT	
11. List the known side effects (these should also be listed in the consent form in this manner): 
 ✓ Likely: none ✓ Less likely: headache ✓ Skin rash (1%) ✓ Diarrhea (2%), vomiting (1%), abdominal pain (<1%), nausea (3%) ✓ Increased liver enzymes AST (1%) ✓ Fever (<1%) ✓ Rare, but serious: <1% : severe allergic reaction with low blood pressure and difficulty breathing, Clostridium difficile-associated diarrhea, confusion, convulsions, decreased visual acuity, depression, liver failure, peripheral neuropathy (may be irreversible), abnormal heart conduction on ECG, rupture of tendon, inflammation in pancreas , low counts 	
12. Describe the precautions used to insure that the risks associated with the administration of this drug/substance is minimized: toxicities will be monitored and dosage will be modified per BMT protocol	

 Yes  No	13. Are there special storage safety or handling conditions required? If yes, please describe:

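### Does the stated 70% power belong to the primary comparison, given that the sizing rates are labelled as overall bacterial infection rather than bloodstream infection to day 60?

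*Combined protocol and SAP*

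**What the plan says.** Section 6 (Project Design and Protocol) gives the primary objective as "to assess incidence of bloodstream bacterial infections in the ciprofloxacin group compared to levofloxacin group up to day 60 after SCT". The same section has patients on ciprofloxacin or "levofloxacin prophylaxis for SCT till engraftment defined as ANC >1000".

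Section 7 (Data Analysis) and section 8 (Justification for Number of Subjects or Data) carry the same sizing sentence: "to prove 10% improvement in overall bacterial infections control (Decrease from 20% to 10" per cent), "need 308 pts; 154 in each group To achieve 70% power". It gives no infection site, time window, alpha or sidedness, and does not say which drug has which rate.

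A few lines later, section 7 describes the purpose of the analysis: "Objectives are to explore the impact of cipro vs levo on Incidence of bacteremia". It then assigns a two-group comparison of proportions to the primary aim.

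Form A for ciprofloxacin, item 10, states the expected benefit as "Prevent infections in neutropenic patients after the conditioning regimen for SCT".

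**The concern.** Read literally, the two rates and the primary test concern different things. Bloodstream infection is a subset of all bacterial infection, so its rate could be lower than 20%. A power figure computed for the broader event need not carry over. Planned power is already only 70%, and a reader who takes the label at face value cannot tell what the real figure is.

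The time window raises a second worry. Prophylaxis stops at engraftment but infections count to day 60. If some bloodstream infections come after the drug has stopped, and neither drug affects them, they dilute the contrast between groups. The sizing sentence does not say whether the assumed halving includes that period. This would suggest restating power over a range of rates and adding a supportive analysis in a fixed early window, for example to day 28. Section 6 uses that landmark when it says "Delayed engraftment is defined as the evidence of engraftment beyond day 28 post SC infusion".

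**Working it through.** **Inputs.** From sections 7 and 8: p1 = 0.20, p2 = 0.10, n = 154 per group, power 70%. Assumed, because not stated: two-sided alpha of 0.05 (z = 1.960).

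**1. Reproduce the plan's figure.** Power of the two-proportion z test with pooled variance under the null:

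power = Φ[(|p1 − p2| − 1.960·SE0) / SE1]

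- mean rate = 0.15; SE0 = √(2 × 0.15 × 0.85 / 154) = 0.0407
- SE1 = √((0.20 × 0.80 + 0.10 × 0.90) / 154) = 0.0403
- power = Φ[(0.10 − 1.960 × 0.0407) / 0.0403] = Φ(0.50) = 69.2%

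Exact enumeration of the same test gives 69.9%. The unpooled sample-size formula gives n = (1.960 + 0.524)² × 0.25 / 0.10² = 154.3 per group, almost exactly the plan's 154. A one-sided 5% level would give 79.4%, so the stated 70% itself points to two-sided 5%. A continuity correction (63.4%) or Fisher's exact test (64.3%) does not match, so the sizing fits the plain two-proportion test that section 7 names. A two-sided test is symmetric, so it does not matter for power which drug carries which rate.

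**2. What if 20% and 10% are not bloodstream rates?** Same formula, n = 154. All rates other than the first row are assumptions.

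| Rates | Relation to the plan | Power |
|---|---|---|
| 20% vs 10% | plan | 69% |
| 16% vs 8% | lower, still halved | 58% |
| 12% vs 6% | lower, still halved | 45% |
| 10% vs 5% | lower, still halved | 38% |
| 18% vs 8% | lower, 10 points kept | 74% |
| 16% vs 6% | lower, 10 points kept | 80% |
| 15% vs 5% | lower, 10 points kept | 84% |

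The spread is wide but has no direction, and the documents give no bloodstream rate that would select a row.

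**3. Which reading do the documents support?** Apart from *Clostridium difficile*, the bacterial outcomes are bloodstream infection (primary), Gram-positive and Gram-negative breakthrough infection (secondary), and bacteremia with resistant and non-resistant Gram-positive strains (section 7). None is an all-site bacterial endpoint for which a 20% rate would be needed. *Overall* therefore contrasts with the Gram-specific outcomes: all organisms combined. On that reading row one applies, and the stated power is that of the primary test.

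**4. What would an early window gain?** Suppose a share f of a 20% day-60 rate is late and unaffected, and the rest is halved. The second group's day-60 rate is 0.20·f + 0.10·(1 − f). An ideal window that catches only the affected events compares 0.20·(1 − f) with 0.10·(1 − f). If the window also catches half of the late events, 0.10·f is added to both rates.

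| f (assumed) | Day 60 | Ideal window | Half of late events caught |
|---|---|---|---|
| 0.1 | 20% vs 11%: 58.9% | 18% vs 9%: 63.8% | 19% vs 10%: 61.2% |
| 0.2 | 20% vs 12%: 48.2% | 16% vs 8%: 58.0% | 18% vs 10%: 52.5% |
| 0.3 | 20% vs 13%: 38.0% | 14% vs 7%: 51.8% | 17% vs 10%: 43.5% |

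The ideal window gains about 5, 10 and 14 points; the imperfect one about 2, 4 and 6. No version reaches 70%.

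**The case for a change.** The strongest case for a change is that the protocol has a specific term for bloodstream infection and did not use it in the sizing sentence, in either place. Nothing visible says that 20% and 10% are day-60 bloodstream rates, and one sentence would settle it. With a planned type II error of 30%, a possible drop to 45% power is not trivial. On the window, the mismatch between the end of prophylaxis and day 60 is real for anyone who engrafts earlier, and a supportive analysis is cheap.

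Part of this stands. The label is loose, and alpha and sidedness are absent from the visible text. But loose wording is not a power error, and the stated power itself identifies the level. The public text also begins at section 4, the data collection tool is described as attached but is not shown, and the sizing sentence in section 8 ends with an asterisk whose note is not visible. The source of the 20% may lie there.

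The window argument is weaker. Infection to a fixed day, the same in both groups, is a legitimate target of estimation. The documents do not say that infections after the drug stops are unaffected by which drug was given, or how many occur. Day 28 is tied to an ANC of 0.5 × 10⁹/L, not to the ANC above 1000 that ends prophylaxis, so it is not the ideal window of the calculation. Breakthrough infection and febrile neutropenia are already secondary outcomes and bear on the period of neutropenia and prophylaxis, although the protocol does not define them or name tests for them. If the day-60 test is not significant, the confidence interval for the difference can still be read; a non-significant early-window result, at 52% to 64% power even in the ideal case, would be no clearer.

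**Conclusion.** The concern does not call for a change. The 70% reproduces (69% to 70% at 154 per group), and it is the power of the primary test on the reading that best fits the text: 20% and 10% are bloodstream infection rates to day 60, all organisms combined. This rests on that reading and on an assumed two-sided 5% level, which the plan's own figure supports. The alternatives run from 38% to 84% power, all on assumed rates and in both directions, so neither an overstatement nor an understatement of power is shown.

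The missing labels are a gap that an analyst fills sensibly. Following the plan as written still gives a comparison of day-60 bloodstream infection proportions between the groups, and the labels alter neither that analysis nor the target of 308. The extra early-window analysis is an option rather than a correction. Its benefit is about 2 to 6 points of power if half the late events fall inside the window, rising to 5 to 14 points only for an ideal window that day 28 is not.

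### The primary aim is tested only with a crude two-proportion test; unless drug assignment is random, transplant mix can distort it, and stratifying by autologous/allogeneic type is a cheap, partial safeguard

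*Combined protocol and SAP*

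**What the plan says.** Section 6 gives the design as "This is a prospective study comparing consecutive patients who will be receiving ciprofloxacin prophylaxis vs. levofloxacin prophylaxis", and the primary objective as "to assess incidence of bloodstream bacterial infections in the ciprofloxacin group compared to levofloxacin group up to day 60 after SCT". Section 7 names one analysis for that objective: "A two sample test of proportion equality will be used as the test for the primary aim". The sample size statement in the same section reads "need 308 pts; 154 in each group To achieve 70% power", for a fall from 20% to 10%.

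Section 5 does not restrict transplant type. Section 6 has one objective for a subset: "In allo SCT patients assess rate of acute graft versus host disease (GVHD) by day 60". Section 7 also says "Demographics, disease-related and transplant-related variables mentioned above will be collected", but gives these variables no role in the primary test.

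The limitations paragraph of section 6 says that uncontrolled variables and their contribution to the "disease course may attenuate the results". It adds: "Sorting and stratifying each variable may create multiple small groups of patients".

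**The concern.** A crude two-proportion test treats the two drug groups as alike apart from the drug. Randomisation would justify that. The available text does not describe randomisation, alternation, calendar blocks or clinician choice.

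Autologous and allogeneic recipients appear to be analysed together. This is an inference from the unrestricted eligibility and the allogeneic-only GVHD objective. If the two types differ in infection risk, and one drug is given to more allogeneic patients, the crude difference contains a part that is not due to the drug.

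The limitations paragraph mentions only attenuation. That is incomplete: unless assignment balances baseline risk, case mix can create, enlarge, hide or reverse a difference. Its worry about small groups applies to separate comparisons within many subgroups. It does not apply to one test pooled over two strata.

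**Working it through.** **Inputs from the documents.** 154 per group; 20% against 10%; 70% power; crude two-proportion test.

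**Assumptions not in the documents.** A two-sided 5% level, infection risk by transplant type, and the allogeneic share in each group.

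**1. The plan's own figure.** Unpooled formula: n = (1.960 + 0.524)² × (0.20×0.80 + 0.10×0.90) / 0.10² = 6.172 × 0.25 / 0.01 = 154.3 per group. The pooled formula gives 157. Exact binomial power of the uncorrected test at 154 per group is 69.9%. A one-sided 5% level would need only about 118 to 120 per group, so two-sided 5% is the natural inference.

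**2. False-positive rate with no drug effect.** With allogeneic share s, a group's risk is s × (allogeneic risk) + (1 − s) × (autologous risk). The spurious crude difference is (mix gap) × (risk gap). For 28%/12% this is 0.10 × 16 = 1.6 points at a 10-point gap and 0.20 × 16 = 3.2 points at a 20-point gap. The crude rates below are exact. The CMH rates come from simulated trials (no continuity correction).

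| Allogeneic share, drug A / drug B | Crude, 28%/12% | Crude, 25%/15% | CMH, both |
|---|---|---|---|
| 50 / 50 | 5.1% | 5.1% | about 5.0% |
| 45 / 55 | 6.5% | 5.7% | about 5.0% |
| 40 / 60 | 10.9% | 7.3% | about 5.0% |
| 30 / 50 | 11.3% | 7.4% | about 5.0% |
| 50 / 70 | 10.6% | 7.2% | about 5.0% |

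If risk does not differ by transplant type, the crude test is not inflated.

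**3. How large a gap chance alone gives.** With a true share of 50% in both groups, the observed shares differ by 10 points or more in 7.7% of trials, by 15 or more in 0.7%, and by 20 or more in 0.05%. Larger gaps therefore need channelling or drift.

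**4. Effect on the estimate.** Let the drug halve risk in each type (28% to 14%, 12% to 6%).
- Higher-risk drug at 30% allogeneic: 0.3×28 + 0.7×12 = 16.8%. Other drug at 50%: 0.5×14 + 0.5×6 = 10.0%. Crude difference: 6.8 points.
- Shares reversed: 20.0% − 8.4% = 11.6 points.
- Difference at the pooled 40% mix: 0.4×14 + 0.6×6 = 9.2 points. The Mantel-Haenszel difference averages 9.1.

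**5. Power of the stratified test.**
- Type prognostic (28%/12%, risk halved), equal shares of 30, 40, 50, 60 and 70%: crude 61.2, 65.6, 69.9, 74.0 and 77.7%; CMH 62.1, 66.6, 71.0, 74.8 and 78.3%.
- Type not prognostic (20% against 10% in both types): CMH 69.7% at equal shares, 67.9% at 40/60 and 61.4% at 20/60, against 69.9% for the crude test.

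**6. Stratum size.** At allogeneic shares of 30% to 70%, the smaller stratum has about 154 × 0.3 = 46 patients per drug. Expected events per stratum, both drugs together, run from 46.2 × (0.12 + 0.06) = 8.3 to 107.8 × (0.28 + 0.14) = 45.3.

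**7. What stratifying does not fix.** Let risk drift from 22% to 18% between successive drug blocks, with equal mixes and no drug effect. The crude test rejects in 14.3% of trials and CMH in about 14.4%.

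**The case against.** The strongest reply is that the premise may be settled in text that is not available. The public document starts at section 4, and Form A, which covers drugs given as part of the research, is compatible with assignment by protocol. If assignment is random, the crude test is valid and a power gain of about one point is a preference. That stands, and it is why the point is conditional.

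The size of the harm also rests on assumptions. The documents give no infection risk by transplant type, no allogeneic share and no sign of unequal mixes. An error rate near 11% needs both a 16-point risk gap and a 20-point mix gap. That stands too.

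A third reply is that the remedy is narrow. If assignment is not random, period and other confounders may matter more, and CMH does nothing about them. This is correct, so the reporting wording has to change as well as the test.

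The authors did consider stratifying and gave a reason against it. That reason does not reach a single two-level stratum.

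A reader might infer that the stratified test is at least as good whatever the assignment. Step 5 shows otherwise: when type is not prognostic it loses a little power, and more as the mixes diverge.

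**Conclusion.** The concern holds in a conditional form. The plan's only primary test ignores transplant type, while the available text gives no assignment rule, appears to pool both types, and collects transplant-related variables. If assignment is not random and the mixes differ, the crude false-positive rate under the assumed risks is 5.7% to 6.5% at a 10-point gap and 7.2% to 11.3% at a 20-point gap, against 5.0% for CMH. If assignment is random, the change is a small efficiency choice.

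The documents do not support the stronger readings that the study is non-randomised, that its groups are unbalanced, or that its primary result will be confounded. They neither show nor exclude these. Nor would stratifying by one binary factor make a non-randomised comparison sound.

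The gap in the plan can be read from the text. Its size rests on the assumed risks, the assumed shares and the inferred two-sided 5% level.

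**What to change.** In section 7, replace the test sentence with:

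> The primary aim will be tested with a Cochran-Mantel-Haenszel test (two-sided 5%, no continuity correction) of bloodstream bacterial infection by day 60, stratified by autologous/allogeneic transplant. The Mantel-Haenszel risk difference will be reported with its 95% confidence interval. The unstratified two-sample test is supportive.

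The level is inferred because it reproduces 308. The continuity correction should be ruled out explicitly: it would cut exact power of the crude test from 69.9% to 64.1%, with a similar cost to CMH.

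In the section 6 limitations, replace the statement about attenuation with: *may bias the comparison in either direction*.

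If assignment is not randomised, add that the result will be reported as an association. If the drugs are used in successive blocks, add that calendar period cannot be separated from drug.

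**Cost.** A few sentences, slightly more analysis and no extra patients. The data form must record transplant type, which the allogeneic-only GVHD objective already needs. If type is not prognostic, power falls by about 0.2 points at equal shares, about 2 points at a 20-point mix gap and about 8 points at a 40-point gap. If the effect differs by type, the Mantel-Haenszel difference is a weighted average that depends on the mix. Only confounding by transplant type is removed.
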